7.4 Statistical tests

Unless otherwise specified, testing effect of dulaglutide on change from baseline will be conducted at a 2-sided alpha level of 0.05, and CIs will be calculated at 95%, 2-sided.

The mixed model for repeated measures method, Negative binomial models, and Cox proportional hazard models techniques will be used.

7.5 Common calculations

Change from baseline will only be calculated for patients with both baseline and post baseline values as:

$$\text{Change from baseline} = \text{postbaseline value} - \text{baseline value}$$

7.6 Software

All analyses will be conducted using SAS® Version 9.4 or later.

8. Statistical considerations

8.1 Multicentre studies

The study will be conducted at multiple centres in India.

8.2 Missing data

For the actual value and change from baseline, a descriptive analysis using LOCF will be performed, using the baseline or 12-week value, if the 24-week value is missing or occurred after use of rescue medication. While performing the mixed modelling with repeated measures (MMRM) Missing data will be assumed missing at random and will be accommodated by the MMRM.

If convergence is not met in the MMRM, the change in HbA1c level from baseline to Week 24 will be analysed using the general linear model and The LOCF method of missing value imputation will be used.

If none of the models converge then an analysis of covariance using LOCF imputation with similar terms as in the MMRM (except no terms that include visit) will be used in its place for body weight, fasting blood glucose, systolic blood pressure, diastolic blood pressure and pulse rate.

9. Output presentations

The templates provided in the separate output templates document describe the format and content for presentation of tables, listings, and figures (TLFs).

Summary statistics will be provided for the observed value and change from baseline will be summarized.

Unless otherwise specified, testing effect of dulaglutide on change from baseline will be conducted at a 2-sided alpha level of 0.05, and CIs will be calculated at 95%, 2-sided.

For continuous measures, summary statistics will include number of patients, mean, SD, median, minimum, maximum, and interquartile ranges for both the actual and the change from baseline measurements. Number of missing values will be specified along with this information.

For categorical measures, summary statistics will include sample size, frequency, and percentages. Number of missing values will be specified along with this information.

10. Participant disposition and withdrawal**10.1 Variables and derivations**

The trial classifications are defined as follows:

- Screening failure:

Individuals who do not meet the criteria for participation in this study (screen failure) may be rescreened after 4 weeks from the date of screen failure after discussion with the medical monitor.

- Completed trial:

A participant is considered to have completed the study if the participant has completed all periods of the study including the last visit.

- Lost to follow-up:

A participant will be considered lost to follow-up if he or she repeatedly fails to return for scheduled visits and is unable to be contacted by the study site. For participants who fail to return for a scheduled visit or were otherwise unable to be followed up by the site, the site personnel or designee is expected to make diligent attempts to contact till 4 weeks from the scheduled visit.

The following parameters will be summarised for the subject's disposition table as per eCRF:

- Number of total screened subjects
- Number of screen failure subjects
- Reason of screen failure subjects
- Number of screen positive subjects
- Subjects who are screened positive but did not receive treatment
- Number of Subject's in Enrolled Analysis set
- Number of Subject's in Full Analysis set
- Number of Subject's in per-protocol analysis set
- Number of Subject's in safety analysis set
- Number of subject's completed trial

- Number of Subject's Completed All Weekly Doses Within Treatment Period
- Number of subjects received 1.5 mg only
- Number of subjects received 0.75 mg only
- Number of subjects with any dose modification* (* subjects who have received at least one dose of 1.5 mg and at least one dose of 0.75 mg)
- Number of subjects withdrew early prior to receiving treatment
- Number of subjects withdrew early from trial
- Subjects who are screened positive but did not receive treatment

The following parameters will be summarised for the early withdrawals table as per eCRF Subject's primary reason for discontinuation (reasons mentioned in eCRF "End of the Study" form) which is as follows:

- Adverse event
- Death
- Lost to follow-up
- Pregnancy
- Protocol violation
- Screen failure
- Consent withdrawal not due to an adverse event
- Site terminated by sponsor
- Study terminated by sponsor
- Withdrawal by sponsor
- Migration from the study site such that follow up visits are not possible
- Other

10.2 Analysis

Population: ENRL

Stratification: Table: Add the strata as needed in case subjects with dose modification exceeding 20% based on enrolled population as per section 7.3:

- a. Subjects on 1.5 mg only
- b. Subjects on 0.75 mg only
- c. Subjects with any dose modification*

* Subjects who have received at least one dose of 1.5 mg and at least one dose of 0.75 mg

Listing: By subject

Statistics: Participant's disposition and Withdrawal will be summarised frequency and percentages and the screen, screening failure subjects will be summarised (frequency) by total for table. The listing will be provided. Protocol deviations will be summarised and presented in listing.

11. Participant demographics and other baseline characteristics**11.1 Variables and derivations**

The following demographic and other baseline characteristics will be summarized:

- Age (Years)
- Gender
- Race
- Ethnicity
- Height (cms) at Screening
- Weight (kgs) at Screening
- BMI (kg/m²) at Screening

11.2 Analysis

Population: FAS

Stratification: Table: Add the strata as needed in case subjects with dose modification exceeding 20% based on enrolled population as per section 7.3:

- a. Subjects on 1.5 mg only
- b. Subjects on 0.75 mg only
- c. Subjects with any dose modification*

* Subjects who have received at least one dose of 1.5 mg and at least one dose of 0.75 mg

Listing: By subject

Statistics: Baseline and Demographic variables will be summarized and listed. Overall summaries will include descriptive statistics for continuous measures (number of patients, mean, SD, median, minimum, maximum, interquartile ranges, number of missing values) and for categorical measures (sample size, frequency, and percentages and number of missing values).

The listing will be presented for diabetes diagnosis data at screening. Summary of duration of type 2 diabetes and associated baseline treatment will be presented.

12. Exposure and Compliance to the treatment

12.1 Variables and derivations

The date of first treatment administration will be derived as the first date of dosing from the exposure eCRF page.

The following parameters will be presented for the exposure summary:

- Number of subjects received first dose
- Number of subjects received weekly doses by each visit
- *Duration of exposure (days) =*
(Date of last treatment administration - Date of first treatment administration) + 1

Compliance will be calculated as follows:

- Compliance with the study treatment (%) = (Actual Dose/ Planned Dose)*100

12.2 Analysis

Population: SAF

Stratification: Table: Add the strata as needed in case subjects with dose modification exceeding 20% based on enrolled population as per section 7.3:

- a. Subjects on 1.5 mg only
- b. Subjects on 0.75 mg only
- c. Subjects with any dose modification*

* Subjects who have received at least one dose of 1.5 mg and at least one dose of 0.75 mg

Listing: By subject and visit

Statistics: The exposure and compliance to the treatment will be summarised and listing will be presented. A plot of dose over time (weeks) per subject will be presented. Listing for deviation from persistence will be provided for the patients who had more than 15 days of gap between two consecutive doses and corresponding dose number.

13. Medical history**13.1 Variables and derivations**

Medical history will be coded using the MedDRA central coding dictionary Version (refer to DMP for dictionary version).

Partial date imputation is not done for medical history.

The following parameters will be summarised for the subject's medical history:

- Number of subjects with at least one medical history
- Number of subjects for each medical history by SOC and PT

13.2 Analysis

Population: SAF and PP

Stratification: Table: Add the strata as needed in case subjects with dose modification exceeding 20% based on enrolled population as per section 7.3:

- a. Subjects on 1.5 mg only by Primary SOC and PT in decreasing order
- b. Subjects on 0.75 mg only by Primary SOC and PT in decreasing order
- c. Subjects with any dose modification* by Primary SOC and PT in decreasing order

* Subjects who have received at least one dose of 1.5 mg and at least one dose of 0.75 mg

Listing: By subject

Statistics: Medical history will be summarised (frequency and percentages) for table and listing also be presented.

14. Prior and concomitant medications

14.1 Variables and derivations

All medications will be coded using the WHO-DD, dated (refer to DMP for dictionary date) All concomitant therapies that was originally mapped using the WHO Drug Dictionary in the ClinTrial database will be further classified using Anatomical Therapeutic Chemical (ATC) codes for reporting purposes.

'Prior medications' are defined as any medication taken prior to first administration of the study treatment.

'Concomitant medications' are defined as any medication taken after or on the day of first administration of the study treatment.

In section 23 Appendix 1 the algorithm is given for calculation of partial date imputation for prior and concomitant medications, and it will be used for partially missing prior and concomitant medications, start and end date imputation.

The following parameters will be summarised separately for each sub-categories (General concomitant medications, rescue therapy and drug used in diabetes) as prior and concomitant medications:

- Number of subjects with at least one prior and concomitant medication
- Number of subjects for each prior and concomitant medication by ATC and PT.

14.2 Analysis

Population: SAF and PP

Stratification: Table: Add the strata as needed in case subjects with dose modification exceeding 20% based on enrolled population as per section 7.3:

a. Subjects on 1.5 mg only by ATC and PT

b. Subjects on 0.75 mg only by ATC and PT

c. Subjects with any dose modification* by ATC and PT

* Subjects who have received at least one dose of 1.5 mg and at least one dose of 0.75 mg

Listing: By subject

Statistics: Prior and concomitant medication will be summarized separately as (frequency, percentages) for table and listing will be presented.

15. Adverse events**15.1 Variables and derivations**

Adverse Events (AEs) will be coded using MedDRA central coding dictionary, Version (refer to DMP for dictionary version).

For the definition of Adverse events (AE) and Serious adverse event (SAE) refer to the protocol section 10.3.

TEAEs are defined as events that are newly reported after the first study drug treatment or are reported to have worsened in severity after the first study drug treatment.

In section 24 Appendix 2 the algorithm is given for calculation of partial date imputation for adverse events (AEs), and it will be used for partially missing adverse event start and end date imputation.

The following parameters will be summarised for the overview of participants' adverse events:

- Any AEs
- Any TEAEs
- Related TEAEs
- Severity of TEAEs (Mild, Moderate, Severe, Life threatening and Death)
- Outcome of AEs (Recovered or resolved, Recovering, or resolving, Not recovered or not resolved, Recovered, or resolved with sequelae, Fatal and Unknown)
- Serious AEs
- AEs leading to Discontinuation from the study
- AEs leading to Death
- Related AEs leading to Death

15.2 Analysis

An overview summary will be presented for TEAEs and SAEs as (n=number of subjects, m=number of events and %=percentage of subjects) by treatment i.e., Dulaglutide, using SAF population.

The listings of Pre-treatment AEs, TEAEs, Serious AEs and AEs resulting in death and AEs leading to study discontinuation will be presented, using SAF population, by treatment group and subject number. AEs will be listed by subject, SOC, Medical Dictionary for Regulatory Activities® PT, severity, outcome, and relationship to the study drug, or procedure for all subjects.

Note: If there are uncoded adverse events, then the uncoded category will be added in the AEs by SOC/PT summary tables.

15.2.1 Incidence of TEAEs, Drug-related TEAE, Serious adverse events (SAEs) and AEs leading to death

Population: SAF and PP

Stratification: Table: Add the strata as needed in case subjects with dose modification exceeding 20% based on enrolled population as per section 7.3:

- a. Subjects on 1.5 mg only by Primary SOC and PT in decreasing order
- b. Subjects on 0.75 mg only by Primary SOC and PT in decreasing order
- c. Subjects with any dose modification* by Primary SOC and PT in decreasing order

* Subjects who have received at least one dose of 1.5 mg and at least one dose of 0.75 mg

Statistics: Treatment emergent AEs, Drug-related TEAE, Serious adverse events (SAEs) and AEs leading to death will be summarized as (n=number of subjects, m=number of events and %=percentage of subjects) for table.

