5.4. Screen Failures

A screen failure occurs when a participant who consents to participate in the clinical study is not subsequently assigned to dulaglutide. A minimal set of screen failure information is required to ensure transparent reporting of screen failure participants to meet the Consolidated Standards of Reporting Trials publishing requirements and to respond to queries from regulatory authorities. Minimal information includes

- demography
- screen failure details
- eligibility criteria, and
- any SAE.

Individuals who do not meet the criteria for participation in this study (screen failure) may be rescreened after 4 weeks from the date of screen failure after discussion with the medical monitor from the Lilly team. Rescreened participants should be assigned a new participant number for every screening or rescreening event.

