9.4. Statistical Analyses

9.4.1. General Considerations

Statistical analysis of this study will be the responsibility of Lilly or its designee. Any change to the data analysis methods described in the protocol will require an amendment only if it changes a principal feature of the protocol. Any other change to the data analysis methods described in the protocol and the justification for making the change will be described in the CSR. Additional exploratory analyses of the data will be conducted as deemed appropriate.

All data will be entered, verified, and archived by a CRO external to Lilly and/or at Lilly. Data listings, summaries, and analyses will be performed by a CRO under the guidance and approval of statisticians at Lilly.

Summary statistics will be provided for the observed value, and change from baseline will be summarized.

Unless otherwise specified, listings will include all enrolled patients. Efficacy analyses will be conducted using the FAS.

Similarly, the exploratory measures (change in body weight from baseline and change in FBG from baseline) will be evaluated in the FAS population.

Also, safety analyses will be conducted on the safety population. The exploratory measures of vital signs (change in SBP, DBP, and pulse rate from baseline) will be analyzed using the safety population).

Unless otherwise specified, testing effect of dulaglutide on change from baseline will be conducted at a 2-sided alpha level of 0.05, and CIs will be calculated at 95%, 2-sided.

For continuous measures, summary statistics will include number of patients, mean, SD, median, minimum, maximum, and interquartile ranges for both the actual and the change from baseline measurements. Number of missing values will be specified along with this information.

For categorical measures, summary statistics will include sample size, frequency, and percentages. Number of missing values will be specified along with this information.

No multiplicity adjustment will be done in this study.

Change from baseline will only be calculated for patients with both baseline and post baseline values as:

$$\text{Change from baseline} = \text{postbaseline value} - \text{baseline value}.$$

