9.4.5. Other Safety Analyses

Laboratory measurements

Continuous chemistry and hematology measures will be summarized by descriptive statistics at baseline and at different visits (Section 1.3) for the safety population.

Continuous chemistry and hematology measures will be summarized as change from baseline to Week 24 using the general linear model, with the baseline value of the response variable as covariate.

All laboratory measurement analyses will be repeated for the Per Protocol population.

AEs analyses

AEs will be listed by

- subject
- SOC
- Medical Dictionary for Regulatory Activities® PT
- severity, and
- relationship to the study disease, drug, or procedure for all subjects.

AEs (including injection-site reactions and neoplasms) will be summarized as TEAEs for the safety population. TEAEs are defined as events that are newly reported after the first study drug treatment or are reported to have worsened in severity after the first study drug treatment. The proportion of subjects experiencing each TEAE will be presented by PT, SOC, and treatment group. The proportion of subjects experiencing each TEAE that is assessed as possibly related to the study disease, drug, or procedures will also be summarized. TEAEs will be summarized by PT within SOC and by PT by decreasing frequency.

All SAEs will be listed by subject and summarized by treatment as counts and percentages. Similar analyses will be performed for discontinuations due to AEs.

All AEs analyses will be repeated for the PPS population.

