6.4 Safety Analysis Set (SAF)

All patients who received at least 1 dose of study treatment.

7. General considerations

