Additionally, all the analysis will be repeated for the below mentioned subgroups:

- age (<65 year and \geq 65 year)
- HbA1c (<8.5 and \geq 8.5)

- Sex (Female and male)
- BMI category (<27 kg/m²) and \geq 27 kg/m²)

21. Other assessments

The listings will be presented for 12-Lead ECG data at screening using SAF population.

The Physical examination assessment will be presented in data listings and summarised as number and percentage (n and %) using SAF population. Physical examination data will be classified as normal and abnormal.

22. Revision history

Version	Date	Change
1.0	19-Dec-2022	Original Document
2.0	19-May-2023	
1. Updated Enroll Population Definition2. Added plots for the HbA1c analysis3. Updated primary and secondary analysis text for the 95% CI presentation in mock shells.4. Added plots vital sign parameters.

23. Appendix 1: Programming Conventions for Tables, Data Listings and Figures (TLFs)

Programs will be developed and maintained and output will be verified in accordance with current risk-based quality control procedures. Tables, figures, and listings will be produced with validated software. The production environment for statistical analysis consists of statistical analysis software; for example, the SAS System version 9.4 or later.

All percentages (%) for a specific summary are calculated using the total number of subjects included in the relevant analysis population as the denominator, unless otherwise specified.

Data listings will be based on all subjects, unless otherwise specified.

In general, if we have no response or record for respective parameter in data (i.e., n=0) then while presenting statistics in table only n will be presented as "0" and other statistics will be left blank. In case we have only one response or record for respective parameter (i.e., n=1) in data then statistic SD in table will be left blank.

By default, for continuous measures, summary statistics will include, unless otherwise specified:

- n
- Mean
- Median
- Maximum
- Minimum
- Standard error
- SD
- Frequency of Missing Values.

For categorical measures, summary statistics will include, unless otherwise specified:

- Frequency of non-missing values
- Percentage, and
- Frequency of Missing Values.

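### SAP 15.2 gives two conflicting populations for its AE and SAE listings, and the section 15 SAE counts have no onset limit, so a lead-in SAE may go unlisted or be counted under dulaglutide

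*SAP*

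**What the plan says.** **Listings.** SAP 15.2 states that "listings of Pre-treatment AEs, TEAEs, Serious AEs and AEs resulting in death and AEs leading to study discontinuation will be presented, using SAF population". SAP 6.4 defines that set as "All patients who received at least 1 dose of study treatment". The next sentence of SAP 15.2 lists AEs by several attributes, ending with "severity, outcome, and relationship to the study drug, or procedure for all subjects". Protocol 9.4.5 has the same scope, "relationship to the study disease, drug, or procedure for all subjects", and adds that every SAE will be listed by subject.

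The general rules do not agree either. SAP section 23 says "Data listings will be based on all subjects, unless otherwise specified", while SAP 23.5 limits listings to treated subjects, again as a default. Protocol 9.4.1 says "Unless otherwise specified, listings will include all enrolled patients". SAP section 5 declares no change from the protocol's analyses.

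**Collection.** Protocol 8.3.1 starts AE collection when consent is signed. Protocol 5.4 says "A minimal set of screen failure information is required to ensure transparent reporting of screen failure participants", and its list of minimum items includes any SAE.

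**Tables.** SAP 15.2.1 says "Treatment emergent AEs, Drug-related TEAE, Serious adverse events (SAEs) and AEs leading to death will be summarized", and 15.2.2 tabulates treatment-emergent AEs and SAEs by severity. In both, only the general AE category is called treatment-emergent. The overview in 15.1 has rows for any AE, serious AEs and AEs leading to discontinuation, none with an onset condition. SAP 15.2 presents the overview under dulaglutide on the SAF. SAP 18.1.1 identifies an SAE by the seriousness answer on the AE form, with no date test.

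**The concern.** A listing of pre-treatment events restricted to people who were later dosed leaves out by construction any event that stopped someone from being dosed. A pre-treatment listing most needs to show those events. A programmer has two adjacent sentences with different populations and two general defaults that disagree, so the output depends on which sentence is followed.

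The tables have the opposite problem. A serious event in the lead-in of a patient who later starts treatment meets every stated condition for the SAE rows and is presented under dulaglutide, although no drug had been given. The study was proposed to document safety for a marketing-authorization condition, and safety is its primary objective. Few SAEs are likely, so one misattributed or omitted case would be noticeable.

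**Working it through.** **1. Which participants can appear in the listings**

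- SAP 15.2, first sentence on listings: SAF, so at least one dose.
- SAP 15.2, next sentence: all subjects.
- Protocol 9.4.5: all subjects for AEs, and every SAE.
- SAP section 23: all subjects by default. SAP 23.5: treated subjects by default.

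Both SAP defaults give way where a section specifies something else. SAP 15.2 specifies two different things, so the defaults cannot settle the matter.

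**2. Whether another output covers untreated participants**

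The disposition and early-withdrawal tables in SAP section 10 use the enrolled set, which SAP 6.1 limits to participants who signed consent and passed screening. Adverse event and death appear there as reasons for leaving, without event term, seriousness or relatedness. No other SAP output clearly lists the events.

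**3. Whether another table covers SAEs in all treated patients with a date limit**

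SAP 18.2.1 restricts AEs and SAEs to Week 0 through Week 24, so that primary proportion is protected. However, SAP 18.1.2 and 18.2.2 name FAS and PP as populations, and the FAS also requires an HbA1c measurement after treatment. Section 15 therefore holds the only SAE tables on all treated patients, and those have no onset limit.

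**4. Which definition of treatment-emergent applies**

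SAP 15.1 counts events newly reported or worsened in severity after first dose. SAP 18.1.1 counts events that started on or after the first dose date. An AE that began in the lead-in and worsened on treatment is treatment-emergent under 15.1 but not under 18.1.1.

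**5. Size**

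The plan's own figures (protocol 9.6) reproduce: 250 × (1 − 0.20) = 200 treated, and 200 × (1 − 0.20) = 160 at the end.

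- One affected patient in the SAF: 1/200 = 0.5 percentage points.
- Pre-dose window: 14 days, or 11 to 17 with the ±3-day tolerance at screening.
- Exposure before dosing in patients later treated: 200 × 14 / 365.25 = 7.67 patient-years.
- The documents give no SAE rate. I assume 2 to 10 SAEs per 100 patient-years, constant over time and fully captured.
- Expected pre-dose SAEs in treated patients: 7.67 × 0.02 = 0.15 to 7.67 × 0.10 = 0.77. Over 11 to 17 days the range is 0.12 to 0.93.
- Expected SAEs from first dose to Week 28, ignoring dropout: 200 × 196 / 365.25 = 107.3 patient-years, giving 2.15 to 10.73.
- Expected SAEs in the 50 people planned as untreated (250 − 200), over 14 days: 50 × 14 / 365.25 = 1.92 patient-years, giving 0.04 to 0.19.

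These pre-dose figures are upper estimates if only procedure-related SAEs are captured. The protocol 8.3.1 row for SAEs before the start of treatment is worded for events judged reasonably possibly related to study procedures.

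**The case against.** The strongest reply is that the plan already limits the damage. The primary proportion is date-limited, the primary incidence formula counts only new events after intervention, the TEAE tables are unaffected, and treated patients' pre-treatment AEs get their own listing. SAP 15.2.1 is headed as an incidence table, and one could carry the post-intervention sense of incidence over from 18.1.1. The detailed table layouts are in a separate templates document that is not available here and may settle the point. All of this narrows the concern, but the SAP text itself sets no limit on the section 15 SAE rows.

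A reader might infer several stronger conclusions that the documents do not support:

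- **Untreated participants' events are reported nowhere.** The sentence extending listings to all subjects, the withdrawal reasons on the enrolled set, and SAE reporting to the sponsor all count against this. The scope of the listings is contradictory; exclusion is not settled.
- **SAP 15.2 breaches protocol 9.4.1.** That rule yields wherever something else is specified, and it covers only screen-positive patients. On the plan's figures all 50 untreated people are screen failures, so the protocol default would omit them too. The conflict is with protocol 9.4.5.
- **A fifth of participants are affected.** The 50 of 250 counts people outside the SAF. It does not measure lost events.
- **Pre-dose events inflate the fatal-AE table.** A treated patient dies after first dose, and a pre-dose AE that becomes fatal has worsened, so it is already treatment-emergent under 15.1. Only the narrower 18.1.1 rule would treat it differently.

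Protocol 5.4 sets a minimum for data collection and does not prescribe a listing. Listing everyone who signed consent is therefore a recommendation that goes beyond the protocol 9.4.1 default.

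**Conclusion.** The point holds as two wording defects. First, SAP 15.2 contradicts itself and protocol 9.4.5 on who appears in the AE, SAE and death listings. If the SAF sentence is followed, an event that prevents dosing cannot be listed. Second, taken literally, the SAE rows in 15.1, 15.2.1 and 15.2.2, and the any-AE and discontinuation rows in 15.1, include events that began before the first dose.

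The likely effect is 0 or 1 SAE. That rests on the assumed 2 to 10 SAEs per 100 patient-years, a 14-day lead-in, 200 treated patients and full capture of pre-dose SAEs. The Week 0 to Week 24 proportion in SAP 18.2 is not affected. The change is still worth making in a trial whose primary purpose is safety reporting, because it removes a possible misattribution and needs only text.

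**What to change.** 1. In SAP 15.2, base the listings of pre-treatment AEs, SAEs and deaths on everyone who signed consent, with a flag for screen failure, enrolled but untreated, or treated. Align the two general listing defaults in SAP 23 and 23.5.
2. In SAP 15.1, 15.2.1 and 15.2.2, restrict the counts of SAEs and of AEs leading to discontinuation to treatment-emergent events. Show pre-treatment SAEs in a separate row or listing, and state which period the any-AE row covers.
3. Use one treatment-emergent definition throughout, reconciling the worsening clause in 15.1 with the start-date rule in 18.1.1. This also settles how fatal AEs that began before the first dose are handled.

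The cost is SAP wording, matching edits to the output templates and a few more listing rows. No new data are needed.
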